14.4 Routine AE Collection and Reporting Guidelines

AEs will be collected from the signing of informed consent until ending study participation. Routine AE reporting will occur via data entry into the study eCRF. AEs will be monitored by the Protocol Management Team (PMT). AEs reported through expedited processes (e.g., reported to the IRB, DSMC, FDA, etc.) must also be reported in routine study data submissions.

AEs recorded in the eCRF include:

- For each cycle and safety follow-up period, all grade 3 and higher AE for each type **AND** the highest grade of AE for each type (if grade 1 or 2)
- All SAEs

14.5 Expedited Reporting

Table 14.5 indicates what events must be reported expeditiously.

Table 14.5 Criteria for Expedited Reporting

Time point	What to report
From signing of the consent to study completion	
• All UPs
From signing of the consent to treatment initiation	
• All SAEs
For the time period beginning at treatment through 30 days following cessation of treatment	
• All SAEs* regardless of relationship to protocol therapy• All UPs and AEs that meet the definition of a UP• Ventricular arrhythmias (Section 14.2.1)• Abnormal liver function tests (Section 14.2.3)• Overdose of acalabrutinib, ublituximab or umbralisib (Section 14.3.1)• Pregnancies and lactation
From Day 1 of protocol therapy up to 2 days post last dose of acalabrutinib and 30 days post last dose of ublituximab or umbralisib	
• Pregnancies and lactation
Post Safety Follow-Up to removal from study	
• All SAEs* that are considered probably or definitely related to acalabrutinib, umbralisib or ublituximab

NOTE: All events reported expeditiously require follow-up reporting until the event is resolved, stabilized, or determined to be irreversible by the investigator.

The DCC should be consulted prior to ending the follow-up of events that have stabilized.

* Refer to [Section 14.7](#) for guidelines on reporting secondary malignancies to the industry partners.

14.5.1 Expedited reporting guidelines (COH only)

14.5.1.1 *To the COH DSMC/IRB*

Serious Adverse Events that require expedited reporting and unanticipated problems will be reported according to the approved [City of Hope Clinical Research Adverse Event and Unanticipated Problem policy](#). This includes all SAEs and UPs that meet COH DSMC/IRB expedited reporting criteria that occurred at COH and non-COH sites.

14.5.1.2 *To Participating Investigators*

- Report all expedited reportable AEs to participating investigators as an IND Safety Report occurring within 30 calendar days of receipt of sponsor (lead site) notification, and indicate whether or not a protocol and/or consent form change is required. A cover letter will indicate the protocol title, the IND#, whether the FDA was informed (if applicable), and, for non-COH sites, a statement that the report should be submitted to their local IRB for review if applicable per local IRB policy.
- Forward to participating sites all IND safety reports received from AstraZeneca and TG Therapeutics, indicating whether a consent form or protocol change is required within 30 days of notification to Study PI.

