14.6 Reporting to the FDA

The study PI (or designee) will be responsible for contacting the Office of IND Development and Regulatory Affairs (OIDRA) at COH to ensure prompt reporting of safety reports to the FDA. OIDRA will assist the PI with the preparation of the report and submit the report to the FDA in accordance with the approved [City of Hope Clinical Research Adverse Event and Unanticipated Problem policy](#).

Serious Adverse Events meeting the requirements for expedited reporting to the Food and Drug Administration (FDA), as defined in [21 CFR 312.32](#), regardless of the site of occurrence, will be reported as an IND safety report using the [MedWatch Form FDA 3500A for Mandatory Reporting](#).

The criteria that require reporting using the MedWatch 3500A are:

- Any unexpected fatal or life threatening adverse experience associated with use of the drug must be reported to the FDA **no later than 7 calendar days** after initial receipt of the information [\[21 CFR 312.32\(c\)\(2\)\]](#)
- Any adverse experience associated with use of the drug that is both serious and unexpected must be submitted **no later than 15 calendar days** after initial receipt of the information [\[21 CFR 312.32\(c\)\(1\)\]](#)
- Any follow-up information to a study report shall be reported **as soon as** the relevant information becomes available. [\[21 CFR 312.32\(d\)\(3\)\]](#)

The final IND report will be distributed to the Study PI and DCC. If it is determined that the IND safety report requires a change to the protocol or the consent form, the DCC will include instructions to participating sites for local IRB reporting.

In addition, on behalf of the study PI, OIDRA will submit annually within 60 days of the anniversary of the date the IND went into effect, an annual report to the FDA which is to include a narrative summary and analysis of the information of all FDA reports within the reporting interval, a summary report of adverse drug experiences, and history of actions taken since the last report because of adverse drug experiences.

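### Section 14.5.1.2 gives participating investigators a 30-day clock even for events that must reach the FDA in 7 or 15 days

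*Combined protocol and SAP*

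**What the plan says.** Section 14.5.1.2 sets the lead site's duty towards the other sites: "Report all expedited reportable AEs to participating investigators as an IND Safety Report occurring within 30 calendar days of receipt". The clock runs from the lead site's own notification. The accompanying cover letter must state, among other things, "whether the FDA was informed (if applicable"), so events that went to the FDA travel in this same mailing. No shorter clock is given for fatal or life-threatening events.

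The second bullet of that section concerns reports from the drug suppliers: "Forward to participating sites all IND safety reports received from AstraZeneca and TG Therapeutics", followed by "indicating whether a consent form or protocol change is required within 30 days of notification to Study PI".

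Section 14.6 sets the FDA clocks and applies them whichever site the event occurred at. For the gravest class the limit is "no later than 7 calendar days", counted from when the information first arrives. The duty for that class reads: "Any unexpected fatal or life threatening adverse experience associated with use of the drug must be reported to the FDA". For the next class, "Any adverse experience associated with use of the drug that is both serious and unexpected must be submitted" within 15 calendar days. The final IND report goes to the Study PI and the Data Coordinating Center (DCC). Sites are mentioned there only for local IRB instructions when the report leads to a protocol or consent change, and no deadline is attached.

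Two other clocks are short. Non-lead sites report to the DCC and Study PI within 24 hours (Section 14.5.2.1), and the Study PI reports to both companies within 24 hours (Table 14.7).

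**The concern.** The trial runs at four sites under one IND. An unexpected death or life-threatening event at one site bears on how the other investigators watch patients already on treatment and on what they tell people who are considering enrolment. The protocol makes each investigator responsible for the safety of subjects in their care (Section 16.1) and treats consent as a continuing process (Section 17.4). Yet for the events that the protocol itself ranks as most urgent, the written deadline for telling those investigators is two to four times as long as the deadline for telling the FDA (30/15 = 2; 30/7 = 4.3).

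Such events are foreseeable. Section 6.2 treats every life-threatening or fatal serious reaction to acalabrutinib as unexpected, and Table 6.2.3 records that fatal hemorrhage and fatal infection have occurred with it. A fatal event attributed to acalabrutinib would therefore meet the 7-day criterion.

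**Working it through.** The plan states no statistical figure on this point, so there is none to reproduce. The check compares deadlines and then sizes the gap.

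**Inputs**
- Notice to participating investigators: at most 30 calendar days (14.5.1.2).
- Notice to the FDA: at most 7 or 15 calendar days (14.6).
- Accrual: about 1 patient per month over all sites (12.3). The maximum of 27 patients in 24 months gives 27/24 = 1.125 per month.
- Cycle length: 28 days (5.1).
- Four participating sites (synopsis).

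**Step 1: gap behind the FDA deadline.** Gap = investigator limit minus FDA limit, assuming that both clocks start on the same day.
- 7-day events: 30 - 7 = 23 days.
- 15-day events: 30 - 15 = 15 days.

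**Step 2: expected accrual in the gap, all sites.** Expected number = monthly rate × days / 30.44. The chance of at least one enrolment, taking arrivals as Poisson, is 1 - exp(-expected number).
- 23 days at 1 per month: 23/30.44 = 0.76; chance 53%.
- 15 days at 1 per month: 15/30.44 = 0.49; chance 39%.
- At 1.125 per month: 0.85 (57%) and 0.55 (43%).

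**Step 3: share at uninformed sites.** The lead site is notified and the originating site already knows. That leaves three of four sites if the event arose at the lead site, and two of four otherwise. The protocol gives no split of accrual by site. Assuming an equal split:
- 23 days: 0.76 × 2/4 = 0.38 to 0.76 × 3/4 = 0.57 patients.
- 15 days: 0.49 × 2/4 = 0.25 to 0.49 × 3/4 = 0.37 patients.

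**Step 4: treatment in the gap.** Both gaps are shorter than a 28-day cycle, so they do not imply that every patient starts a new cycle uninformed. Acalabrutinib is taken daily (5.3), however, so dosing continues throughout.

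**Step 5: is there an earlier guaranteed route to the sites?**
- Toxicity monitoring (12.4.2) looks once after the sixth patient's first cycle, then every 6 months. It halts accrual only if more than 1 of the first 6 patients, or later at least 33%, have listed events. A single death need not trigger it.
- Site investigators belong to the Protocol Management Team (PMT, 16.3), but its meetings are only recommended and no frequency is set.
- Registration is central (4.2), but nothing ties it to a safety report, and it does not reach sites whose patients are already on treatment.

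None of these sets a deadline for informing sites.

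**Step 6: supplier reports.** In the second bullet of 14.5.1.2, the 30 days may govern the forwarding itself or only the statement on consent or protocol change. On the first reading forwarding may take 30 days. On the second no forwarding deadline is stated.

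**The case against.** The strongest reply is that different recipients may properly have different deadlines, and that 30 days is a ceiling. The site mailing is more than a copy of the FDA report: it must say whether the protocol or consent form needs to change and carry local IRB instructions, and that takes time. Every enrolment also passes through the DCC, with slots held at the Study PI's discretion, and both are told of events at other sites within 24 hours. Enrolment at an uninformed site is thus controlled by informed people.

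Much of this stands. It limits the finding to a permitted delay and means that the fix must separate the first notice from the change determination. It does not explain why the first notice of an FDA-reportable event should wait for that determination.

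A reader might also infer more than the documents support:
- **That the 30-day clock breaches 21 CFR 312.32.** Section 14.6 recites only the clocks for reporting to the FDA. What the regulation says about notifying investigators is not in the documents, so no such claim is made here.
- **That all events in the 30-day mailing are affected.** Table 14.5 also covers SAEs regardless of relationship, overdoses, pregnancies and liver-test findings, many of which have no 7- or 15-day FDA clock.
- **That treating sites are told last.** The lead and originating sites are treating sites and already know. The timing of reports to the DSMC and IRB follows an institutional policy not reproduced in the protocol.
- **That a full further cycle and about one new patient are at stake.** Those figures use all 30 days (30/30.44 = 0.99 patients). The excess over the FDA clock is 23 or 15 days.

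**Conclusion.** The point holds for the FDA-reportable subset. As written, the protocol lets investigators at two or three of the four sites learn of such an event up to 23 days (unexpected fatal or life-threatening) or 15 days (other serious unexpected) after the FDA deadline. They may dose and consent patients in that time without the information. Expected accrual in the gap is about 0.76 or 0.49 patients over all sites, and less at the uninformed sites alone.

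This rests on the full 30 days being used, on the two clocks starting together, and on the planned accrual rate. It is an internal mismatch in safety communication that should be corrected. It affects no endpoint, analysis or stopping rule. The supplier-report limb is less certain, because the sentence is ambiguous.

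**What to change.** In Section 14.5.1.2:
- Send the initial report of any event meeting the Section 14.6 criteria to all participating investigators no later than it goes to the FDA: at most 7 calendar days for unexpected fatal or life-threatening events and 15 for other serious unexpected events.
- Forward supplier IND safety reports that meet the same criteria within the same limits, counted from receipt by the Study PI. Reword the second bullet so that it is clear what its 30 days governs.
- Keep 30 days for all other expedited events, and for the follow-up statement on whether a protocol or consent change is required.

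The report already exists once it goes to the FDA, so the extra work is sending it to at most three further sites. The small downside is that the first notice and the change determination may go out as two mailings. The wording change itself needs the usual amendment route, including approval by both companies (Section 16.7).

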14.5.2 Expedited reporting guidelines (non-COH sites only)

14.5.2.1 *To the DCC/Study PI*

All events that meet the criteria specified in Table 14.5 will be reported to the DCC and Study PI within 24 hours of notification that the event met the expedited reporting criteria.

1. Sites are to report to their local IRB per their site's specific institutional and IRB guidelines. As soon as possible, non-COH sites will provide to the COH DCC copies of the IRB submission and corresponding IRB response.
2. Document/describe the AE/UP on each of the following:
 - a. MedWatch 3500A or local IRB submission document*
MedWatch 3500A is downloadable form at <http://www.fda.gov/medwatch/getforms.htm>
*The local IRB submission document may be used if the document template is approved by the DCC
 - b. Expedited Reporting Coversheet. A modifiable Microsoft Word document is available from the DCC. An electronic signature on the document will be accepted.
3. Scan and email above documents to the Study PI ([contact]) and [contact] with the subject title as “[AU2 for previously untreated MCL] SAE COH IRB #20459”.
 - a. If available, sites may include the local IRB submission for this event in the submission.
4. If an email receipt from DCC personnel is not received within one working day, please email [contact].

14.6 Reporting to the FDA

The study PI (or designee) will be responsible for contacting the Office of IND Development and Regulatory Affairs (OIDRA) at COH to ensure prompt reporting of safety reports to the FDA. OIDRA will assist the PI with the preparation of the report and submit the report to the FDA in accordance with the approved [City of Hope Clinical Research Adverse Event and Unanticipated Problem policy](#).

Serious Adverse Events meeting the requirements for expedited reporting to the Food and Drug Administration (FDA), as defined in [21 CFR 312.32](#), regardless of the site of occurrence, will be reported as an IND safety report using the [MedWatch Form FDA 3500A for Mandatory Reporting](#).

The criteria that require reporting using the MedWatch 3500A are:

- Any unexpected fatal or life threatening adverse experience associated with use of the drug must be reported to the FDA **no later than 7 calendar days** after initial receipt of the information [\[21 CFR 312.32\(c\)\(2\)\]](#)
- Any adverse experience associated with use of the drug that is both serious and unexpected must be submitted **no later than 15 calendar days** after initial receipt of the information [\[21 CFR 312.32\(c\)\(1\)\]](#)
- Any follow-up information to a study report shall be reported **as soon as** the relevant information becomes available. [\[21 CFR 312.32\(d\)\(3\)\]](#)

The final IND report will be distributed to the Study PI and DCC. If it is determined that the IND safety report requires a change to the protocol or the consent form, the DCC will include instructions to participating sites for local IRB reporting.

In addition, on behalf of the study PI, OIDRA will submit annually within 60 days of the anniversary of the date the IND went into effect, an annual report to the FDA which is to include a narrative summary and analysis of the information of all FDA reports within the reporting interval, a summary report of adverse drug experiences, and history of actions taken since the last report because of adverse drug experiences.

14.7 Reporting to Industry Partners

The Study PI (or designee) will:

- Report the following to AstraZeneca and TG Therapeutics per the guidelines provided in Table 14.7 below.
 - AstraZeneca: email: [contact]
 - TG Therapeutics: email: [contact], (copy [contact] and [contact])
- Assist AstraZeneca/ TG Therapeutics in investigating any SAE and will provide any follow-up information reasonably requested by AstraZeneca/ TG Therapeutics.

Table 14.7 Timeframes for Reporting to AstraZeneca/ TG Therapeutics

Type of Report	Reporting Timeframes to AstraZeneca	Reporting Timeframes to TG Therapeutics
Pregnancy and suspected pregnancy	Pregnancy and suspected pregnancy: Within 24 hours of being aware of the event using a Pregnancy Report Form	Pregnancy (including of male participant partner), pregnancy outcome with 6-month follow up from end of pregnancy (birth, abortion [spontaneous, accidental or therapeutic], voluntary termination, etc.): Within 24 hours of being aware of the event using a Pregnancy Report Form
All expedited SAE reports (includes AESIs [specified in Section 14.2]) Note: See below for guidelines on reporting secondary malignancies.	Within 24 hours of being aware of the event via a MedWatch 3500A form. Note: Overdose of acalabrutinib should be reported as an “overdose” report. If there is an associated AE/SAE, this should be reported too.	Within 24 hours of being aware of the event via a MedWatch 3500A form including SAEs experienced during pregnancy and congenital anomalies/birth defects.
Aggregate safety reports	Forward to AstraZeneca at time of COH PMT report: [contact]	Forward to TG Therapeutics at time of COH PMT report: [contact] [contact] [contact] [contact]

- Reporting of secondary malignancies
 - AstraZeneca:

Adverse Events (AEs) for malignant tumours reported during the study should generally be assessed as Serious AEs. If no other seriousness criteria apply, the 'Important Medical Event' criterion should be used. In certain situations, however, medical judgement on an individual event basis should be applied to clarify that the malignant tumour event should be assessed and reported as a Non-Serious AE. For example, if the tumour is included as medical history and progression occurs during the study, but the progression does not change treatment and/or prognosis of the malignant tumour, the AE may not fulfill the attributes for being assessed as Serious, although reporting of the progression of the malignant tumor as an AE is valid and should occur. Also, some types of malignant tumours, which do not spread remotely after a routine treatment that does not require hospitalization, may be assessed as Non-Serious; examples include Stage 1 basal cell carcinoma and Stage 1A1 cervical cancer removed via cone biopsy. For studies in Early Stage and Late Stage Immuno-Oncology and Oncology Studies: The above instruction applies only when the malignant tumour event in question is a new malignant tumour (i.e., it is not the tumour for which entry into the study is a criterion and that is being treated by the IP under study and is not the development of new or progression of existing metastasis to the tumour under study). Malignant tumours that – as part of normal, if rare, progression – undergo transformation (e.g., Richter's transformation of B cell chronic lymphocytic leukemia into diffuse large B cell lymphoma) should not be considered a new malignant tumour.

- TG Therapeutics: Secondary malignancies do not need to be reported as SAEs to TG Therapeutics.
- Forward to AstraZeneca and TG Therapeutics copies of initial/annual/final FDA IND submissions. Email: [contact] and [contact].

15.0 ADHERENCE TO THE PROTOCOL & REPORTING OF PROTOCOL DEVIATIONS

Deviations from the protocol should be avoided, except when necessary to eliminate immediate hazard(s) for the protection, safety, and well-being of a research participant. As a result of deviations, corrective actions are to be developed by the study staff and implemented promptly. All protocol deviations and planned protocol deviations will be reported in accordance with the [City of Hope Clinical Research Protocol Deviation policy](#).

Non-COH Sites:

Deviations meeting the criteria specified in the City of Hope Clinical Research Protocol Deviation policy (available from the DCC) will be reported to the DCC and Study PI within **24 hours** of notification that the event occurred.

Procedure for reporting deviations to the COH DCC:

1. Document the deviation on the Deviation Reporting Coversheet or submit your site-specific protocol deviation log if the log format has been approved for use by the DCC. This modifiable Microsoft Word document is available from the DCC. An electronic signature on this document will be accepted.
2. Scan and email the Deviation Reporting Coversheet or protocol deviation log to the Study PI ([contact]) and [contact] **within 24 hours** of notification of the deviation with the email subject title of “[AU2 for previously untreated MCL] Deviation COH IRB #20459”. If

an email receipt from the DCC is not received within one working day, please email [contact].

3. Sites are to report to their local IRB and DSMC per their site's specific institutional and IRB guidelines. As soon as possible, non-COH sites will provide to the COH DCC copies of the IRB and/or DSMC submission and corresponding response(s).

16.0 STUDY OVERSIGHT, QUALITY ASSURANCE, & DATA AND SAFETY MONITORING

16.1 All Investigator Responsibilities

An investigator is responsible for ensuring that an investigation is conducted according to the signed investigator statement, the investigational plan, and applicable regulations; for protecting the rights, safety, and welfare of subjects under the investigator's care; and for the control of drugs under investigation.

16.2 Study Principal Investigator Responsibilities

The Study Principal Investigator is responsible for the conduct of the clinical trial, including overseeing that sponsor responsibilities are executed in accordance with federal regulations.

16.3 Protocol Management Team (PMT)

The Protocol Management Team (PMT), minimally consisting of the study PI, collaborating investigators, site investigators, research nurse, clinical research associate/coordinator, and the study biostatistician, is responsible for ongoing monitoring of the data and safety of this study, including implementation of the stopping rules for safety/toxicity.

The PMT is recommended to meet (in person or via teleconference) to review study status. The meeting is a forum to discuss study related issues including accrual, SAE/AE/UPs experienced, study response, deviations/violations, and study management issues. The appropriateness of further subject enrollment and the specific intervention for subsequent subject enrollment are addressed.

